- Willing to refrain from using any other topical products on the face, systemic retinoids, or steroids, facial peels or other facial laser procedures throughout the duration of the study
- Willing to refrain from any cosmetic procedure including but not limited to facial surgery, dermal fillers, and neuromodulators for the duration of the study
- Willing to use only the facial skin care product regimen provided for the study
- Willing to avoid extended periods of sun exposure and the use of tanning beds during the study
- Willing to have photographs taken of the face to be used de-identified in evaluations, publications, and presentations
- For females: proof that they are not pregnant (urine pregnancy test)
- English-speaker

Exclusion criteria:

- Has any uncontrolled systemic disease (such as autoimmune disorders and

connective tissue disorders such as lupus erythematosus or Sjogren's syndrome
Has any active infection in face
Has history of any skin conditions that could interfere with treatment
Has used self-tanner recently
Is currently participating in another drug research study
Is NOT willing to refrain from using any other topical products such as skin lightening, retinoids, alpha/beta-hydroxyl acids, salicylic acid, vitamins C or D, steroids, or antibiotics on the face or systemic retinoids, steroids, facial peels, neuromodulators, dermal fillers, facial surgery, or other facial laser procedures throughout the duration of the study
For females: is pregnant
Non English-speaker

Individuals will be screened for eligibility via questionnaires that address each of the inclusion and exclusion criteria. Our final study sample will include the subjects who met the inclusion/exclusion criteria and did not voluntarily drop out of the study or develop adverse effects that prohibited them from safely completing the study. We will exclude adults unable to consent, patients under the age of 18, pregnant women, and prisoners.

5) Number of Subjects*

After recruiting our subjects, 14 patients will be randomized into either arm of the study (7 in each arm).

6) Study-Wide Recruitment Methods*

This is a single center study. We will recruit subjects from a clinical database of the practice of [name]. We will use several recruitment methods including invitation via a scripted email providing information describing the study protocol and end-points, scripted invitation telephone calls, and flyers.

7) **Study Timelines***

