	Screening/Baseline Visit 1	Washout period	Visit 2 First Laser treatment (4 weeks +/- 5 days after baseline visit)	Visit 3 Second Laser Treatment (3 weeks +/- 5 days after first laser treatment)	Visit 4 Last day of topical treatment (4 weeks +/- 5 days after second laser treatment)
Procedures					
Informed Consent	X				
Inclusion/Exclusion criteria	X				
Demographic History Questionnaire	X				
Medical History Review	X				
Skincare History Review	X				
Evaluate Fitzpatrick skin type	X				
Evaluate baseline hyperpigmentation	X				
Urine dipstick test	X		X	X	X
Self assessment questionnaire	X				X
Standardized Digital photography	X		X	X	X
Adverse effects review	X		X	X	X
MoPASI evaluation	X		X	X	X
GAIS evaluation	X		X	X	X
Anesthetizing topical application			X	X	X
Protective goggles placed			X	X	
Laser treatment performed			X	X	
Exit Questionnaire					X

Potential participants will receive a thorough history and dermatologic physical exam to determine if patients meet the inclusion/exclusion criteria for being in the study. Urine dipstick tests will be performed on female

patients to confirm they are not pregnant. Consent will be obtained from eligible participants and will be enrolled in the study.

The study will be conducted over a 12 week period. There will be a 4 week washout period prior to laser treatments when the subjects will begin two skin care regimens, which are described below. Then there will be 2 laser treatments separated by 3 weeks. The subjects will continue the topical treatment 1 month after the 2nd laser treatment.

There will be 4 study visits: Baseline Visit 1, First laser treatment Visit 2 (4 weeks +/- 5 days after baseline visit), Second laser treatment Visit 3 (3 weeks +/- 5 days after first laser treatment), and Last day of topical treatment Visit 4 (4 weeks +/- 5 days after second laser treatment). During these visits, photographs of the participants' faces will be taken. Patient questionnaires will be given at baseline and at the end of the study.

Investigators will complete the study 4 months after subjects have completed their participation in the study.

8) Study Endpoints*

The study will reach endpoint for each patient either 1) once they have completed their exit survey after the 2 laser treatments and the topical treatments or 2) if they experience any adverse reactions from treatment and must be pulled from the study.

9) Procedures Involved*

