Local tolerability including itching, redness, burning, or pain will be assessed at each visit by the investigator. Subjects will also be asked to assess discomfort during treatment and also to maintain diary at home to record any side effects after each facial laser treatment. To lessen the probability of risks of laser treatment, will use the standard pulse energy and coverage known to produce the minimal amount of side effects, increase subject comfort, and allow for rapid healing.

Once all subjects have completed the study, one independent evaluator will retrospectively analyze the VISIA high definition photography data that was taken at each visit. The independent observer will evaluate the photos of each patient for clinical efficacy and tolerability using two validated grading scales (Modified Pigmentation Area and Severity Index (MoPASI) and Global Aesthetic Improvement Scale (GAIS)) at baseline and at weeks 5, 8, and 12.

The GAIS is used to evaluate change in aesthetics after intervention. 0 = worse, 1 = no change, 2 = improved, 3 = much improved, 4 = very much improved. The MoPASI is a dermatologist-developed modified scale derived from the validated Melasma area and severity index scale. Pigmentation is assessed in 4 sections of the facial skin, and three variables are assessed within each region: percentage of area involved, darkness of pigment in the area, and pattern of involvement in the area. Subjects will complete self-

assessment questionnaires at baseline and at the end of the study.

The Clear and Brilliant 1927nm laser has been used extensively in facial cosmetic surgery for skin resurfacing to improve the skin changes associated with photoaging and skin tone. The laser is FDA approved for this use (see Device attachments for documentation). The Solta Medical Company has proven that it produces safe and effective treatment and even in combination with topicals, has a high safety profile (see supporting documents).

Lytera 2.0 Correcting Serum, a Skin Medica product, is a non-hydroquinone, non-drug advanced Correcting Serum that has been proven to minimize the appearance of skin discoloration and dark spots. Our proposed study is to observe the effect of Lytera 2.0 on skin tone, and will not evaluate any underlying changes to skin structure or function. The assessments in the proposed study are observational and do not include biopsy or other method.

Key ingredients of Lytera 2.0 Pigment Correcting Serum:

Tranexamic Acid

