Phenylethyl Resorcinol

Niacinamide and Tetrapeptide 30

Marinen Extract blend

Phytic Acid

Other ingredients: Vitis Vinifera SCE, Plankton Extracts, Hydroxyacetophenone, Artemisia Capillaris, Marine Exopolysaccharides

Data that will be collected about subjects (see attached data collection form):

Age

Gender

Race

Past medical history including current and past illnesses, current medications, allergies, past surgeries, any past adverse effects to facial cosmetics, family history, social history including alcohol, tobacco, or illicit drug use.

Past skin care history including any surgical cosmetic procedures, fillers, injectables, lasers, or topical treatments.

Fitzpatrick skin type (I-IV)

Evaluation of baseline skin tone

Adverse effects experienced throughout the study

MoPASI scores

GAIS scores

Representative photographs of subjects at baseline and at subsequent visits

10) **Data and Specimen Banking***

Data will be stored on Box, a secure file sharing, storage, and collaboration system using a password-protected, encrypted laptop. Data will be stored for 1 year after the completion of the study. Only [name], principal investigator and [name] and [name], co-investigators and study coordinator will have access to the data. Data will only be released by Drs. [name] or [name] for publication of study results.

Stored data will include:

Age

Gender

Race

Past medical history including current and past illnesses, current medications, allergies, past surgeries, any past adverse effects to facial cosmetics, family history, social history including alcohol, tobacco, or illicit drug use.

Past skin care history including any surgical cosmetic procedures, fillers, injectables, lasers, or topical treatments.

Fitzpatrick skin type (I-IV)

Evaluation of baseline skin tone

Adverse effects experienced throughout the study

MoPASI scores

GAIS scores

Representative photographs of subjects at baseline and at subsequent visits

11) **Data Management***

Statistical analysis will be conducted to determine the effect size necessary to power a study. All statistical tests will be two-sided and interpreted at a 5% significance level. The primary analyses will be based on the MoPASI and GAIS scores. Scores after each laser treatment will be compared to baseline scores using the appropriate statistical test.

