Data will be secured and stored on Box, a secure file sharing, storage, and collaboration system using a password-protected, encrypted laptop.

Information that will be included in data include demographic information, skin type, baseline hyper pigmentation, adverse effects, validated scale scores, photographs, past medical and skin care history as listed above.

Data will be stored in Excel sheet on the encrypted system, Box, which will

give us access to the data via an encrypted stream of traffic. No actual copy of the data will be stored on a machine. Data will be stored for a short-term retention period of 5 years or less at the location [name]. The principal and co investigators will have access to the data. Drs. [name] and [name] will be responsible for transmission of data. Data will be transported via laptop. Aforementioned laptop will be completely shut down after all browser data has been cleared before being transported or left unattended. In addition to the data encryption, a passcode into the device will be required.

12) Provisions to Monitor the Data to Ensure the Safety of Subjects*

The physician investigators and the subjects themselves will monitor the type, severity, duration, and frequency of adverse effects during treatment. Adverse effects will be evaluated by investigator at each visit. Subjects will fill out diary while at home to record any adverse effects. Investigator will be accessible to subjects via email and phone to answer questions about any adverse effects. Safety data and efficacy data (based off of validated scale scores) will be reviewed after each visit. Safety information will be collected at study visits and by email communication with participants. Safety data collection will begin on day 1 of the washout period when subjects begin the skin care regimen. The investigators will review the data at each visit and as needed. Safety information that will be collected includes pain, visual disturbance, rash, fever, infection, photosensitivity, scarring, and changes in skin color.

If a patient becomes pregnant, develops severe post-inflammatory skin tone, or experiences an anaphylactic or other severe allergic reaction, they will be pulled from the study. If they exhibit any of the "exclusion criteria" after initial evaluation of eligibility for participation in study, they will also be removed from the study.

13) Withdrawal of Subjects*

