If a patient becomes pregnant, develops severe post-inflammatory skin tone, excessive scarring, burning, or experiences an anaphylactic or other

severe allergic reaction or infection requiring antibiotic treatment, they will be pulled from the study.

If they exhibit any of the “exclusion criteria” after initial evaluation of eligibility for participation in study, they will also be removed from the study.

Exclusion criteria:

Has any uncontrolled systemic disease (such as autoimmune disorders and connective tissue disorders such as lupus erythematosus or Sjogren's syndrome

Has any active infection in face

Has history of any skin conditions that could interfere with treatment

Has used self-tanner recently

Is currently participating in another drug research study

For females: is pregnant

Non English-speaker

Participants that develop criteria for withdrawal from the study or any potential side effect will be examined in the office. Participants that meet criteria for withdrawal from treatment will be informed during office visit. Safety information will still be collected until week 12 of the study.

14) Risks to Subjects*

Side effects of Lytera topical include stinging or tingling on application, redness, and general irritation in those with sensitive skin.

There are some expected side effects of the Clear and Brilliant facial laser procedure. These may include discomfort, redness, swelling, heat sensation, dark spots, flaking, itching, acne formation, herpes simplex reactivation, blistering, and dryness. Patients can expect facial redness immediately after treatment that commonly resolves within a few hours but may last until the next day in some patients. Possible risks or complications associated with this facial laser procedure include bleeding or crusting, burns, scarring, pigment changes, infection, and eye injury. It has been shown that adverse effects typically resolve without discontinuation of the products. There may be psychological risks associated with treatments as patients may feel self-conscious about erythematous face for a couple days

after the laser treatments. If subjects experience any of the aforementioned side effects, this may also be distressing.

Potential risks of combination Clear and Brilliant laser and Lytera treatment include all of the side effects listed above.

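### Sections 12 and 13 give different mandatory withdrawal lists, and Section 13's undefined burning trigger overlaps a routine tolerability item, so removals, and through Section 4 the analysed sample, are open to interpretation

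*Combined protocol and SAP*

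**What the plan says.** Section 12 (safety monitoring) removes a subject who becomes pregnant, and one who "develops severe post-inflammatory skin tone, or experiences an anaphylactic or other severe allergic reaction, they will be pulled from the study". It also removes anyone who later meets an exclusion criterion.

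Section 13 (withdrawal) repeats that rule with more triggers. After pregnancy it names a subject who "develops severe post-inflammatory skin tone, excessive scarring, burning, or experiences an anaphylactic or other" severe allergic reaction, and it adds infection that needs antibiotics. It repeats the sentence on meeting any exclusion criterion and then reprints the list. The reprint leaves out the Section 4 item on being unwilling to refrain from other products and procedures. After withdrawal, Section 13 provides for safety information up to week 12 and does not mention MoPASI or GAIS.

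Three other sections bear on this:

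- Section 9: "Local tolerability including itching, redness, burning, or pain will be assessed at each visit by the investigator".
- Section 14 lists stinging, tingling, redness and irritation for the serum, and heat sensation among the expected laser effects. Burns and scarring appear separately as possible complications. It then says: "It has been shown that adverse effects typically resolve without discontinuation of the products".
- Section 4 limits the final sample to eligible subjects who "did not voluntarily drop out of the study or develop adverse effects that prohibited them from safely completing the study".

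**The concern.** Both lists are worded as mandatory, and nothing says which governs. A subject with burning or excessive scarring after the first laser session must leave under Section 13 but meets no trigger named in Section 12. An investigator working from Section 12 alone could keep that subject in and go on to the second session.

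The word burning adds to the problem. The same word names a tolerability item reviewed at every visit and a reason for compulsory exit, with no stated threshold between them.

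The analysis is exposed because Section 4 ties the final sample to safe completion. Only one arm receives the serum, irritation is among its listed effects, and no blinding of the treating investigators is described. An undefined trigger applied with judgement could therefore remove subjects unevenly between arms, and the comparison would then rest on those who tolerated treatment.

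**Working it through.** **Comparison of the two lists**

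| Trigger | Section 12 | Section 13 |
|---|---|---|
| Pregnancy | yes | yes |
| Severe post-inflammatory skin tone | yes | yes |
| Anaphylactic or other severe allergic reaction | yes | yes |
| Excessive scarring | not named | yes |
| Burning | not named | yes |
| Infection needing antibiotics | facial infection only, through the exclusion criteria | yes |
| Any exclusion criterion | yes | yes, but the reprinted list is one item short |

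Active infection of the face is an exclusion criterion in Section 4, so Section 12 already covers it. On infection, the sections differ only for infections elsewhere that need antibiotics.

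**Inputs.** Section 5 gives 7 subjects per arm, 14 in all. Section 11 states: "All statistical tests will be two-sided and interpreted at a 5% significance level". The documents give no SD, effect size, dropout allowance or burning rate, so there is no planned figure to reproduce. What follows is illustration.

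**Weight of one subject.** 1/7 = 14.3% of an arm; 1/14 = 7.1% of the trial.

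**Precision.** Assume 0 to 3 removals, all in one arm, and a pooled two-sample t interval. In units of the common SD, the half-width is t(0.975, n1 + n2 − 2) × √(1/n1 + 1/n2).

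- 7 v 7: 2.179 × √(1/7 + 1/7) = 2.179 × 0.5345 = 1.16
- 7 v 6: 2.201 × √(1/7 + 1/6) = 2.201 × 0.5563 = 1.22
- 7 v 5: 2.228 × √(1/7 + 1/5) = 2.228 × 0.5855 = 1.30
- 7 v 4: 2.262 × √(1/7 + 1/4) = 2.262 × 0.6268 = 1.42

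**How often the literal rule would act.** If a proportion p of subjects report burning of any degree, Section 13 read literally removes 14p on average, and at least one with probability 1 − (1 − p)^14.

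| Assumed p | Expected removals of 14 | Chance of at least one |
|---|---|---|
| 5% | 0.7 | 51% |
| 10% | 1.4 | 77% |
| 20% | 2.8 | 96% |
| 30% | 4.2 | 99% |

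On this trigger, Section 12's named list removes none.

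**The case against.** The strongest reply is that the lists are nested. Section 13 contains everything in Section 12, it is the section headed as governing withdrawal, and Section 12 does not claim to be exhaustive. On that view Section 12 is an incomplete repetition. This stands in part: the lists do not oppose each other. But both are mandatory, neither refers to the other, and Section 12 is the section that governs safety review at each visit.

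Burning may also not mean a symptom. Section 14 pairs burns with scarring as complications, and Section 13 puts scarring and burning side by side. The qualifier on scarring may also be meant to cover burning. Either reading is plausible and the text settles neither, so it is not established that a routine symptom was intended as a trigger. Section 9 says burning is assessed and describes no grade that would separate the two.

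Two stronger readings are tempting and are not supported:

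- A reader might take Section 8 as a third rule that removes subjects for any adverse reaction. Its wording is "if they experience any adverse reactions from treatment and must be pulled from the study". The condition is joint, and who must be pulled is left to other sections. It is vague rather than a separate rule.
- A reader might infer that someone who starts a prohibited product is removed under Section 12 but kept under Section 13. The omitted item concerns willingness, and Section 13's lead sentence still covers any exclusion criterion. Section 4's description of the final sample names voluntary dropout and adverse effects, so an effect of this omission on the analysed sample is not shown.

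Finally, the half-widths measure precision, not bias, and Section 11 plans comparisons with baseline by an unnamed test. Both points are fair; the figures show only how little loss 7 per arm can absorb.

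**Conclusion.** The inconsistency holds between Sections 12 and 13. Only Section 13 names excessive scarring and burning, and its burning trigger is undefined. Because Section 4 makes the final sample depend on safe completion, the reading chosen can change who is analysed.

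The size is one subject per 14% of an arm, and a half-width that grows from 1.16 to as much as 1.42 SD. That range rests on an assumed 0 to 3 removals confined to one arm, a common SD and a between-arm t interval. The burning rates used above are likewise assumptions.

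A reader might infer that the comparison will be biased against or in favour of the serum. The documents do not support that. They give no rates by arm, and show only that uneven removal is possible. Nor would a single agreed list remove that risk by itself, because it arises from Section 4's restriction to completers.

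**What to change.** 1. Sections 12 and 13 must be reconciled into one withdrawal list that both cite, with Section 8 pointing to it.
2. That list should state whether the burning that triggers withdrawal is the same event assessed as local tolerability in Section 9, and whether the exclusion item missing from Section 13's reprint applies. Which clinical rule applies is for the investigators to decide.
3. Record the reason for each withdrawal and report it by arm.
4. Amend Section 4 so that MoPASI and GAIS scores already collected from withdrawn subjects stay in the analysis by randomised arm. Section 9 has photographs taken before the laser at Visits 2 and 3. A subject withdrawn between those visits may therefore have no post-laser score; the report should say how many such subjects there are in each arm.

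The cost is protocol wording and one entry on the data collection form. No visits or staff are added.

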One month prior to laser treatments (washout period), 14 male and female subjects with moderate hyper pigmentation and photo damage of the face will be randomized to 2 skincare regimens.

The regimens are:

- "Placebo arm" – Basic skin care regimen* (Facial Cleanser, TNS ceramide Treatment Cream (standard post-procedure moisturizer), and Essential Defense Mineral Shield Broad Spectrum SPF35 (all-physical sunscreen))
- "Lytera arm" – Basic skin care regimen + **Lytera 2.0**, which will be added between the Facial Cleanser and TNS Ceramide Treatment Cream

*The basic skin care regimen is a standard regimen used in several skincare product experiments

After cleansing the face, the patients in the Lytera arm will apply one pump of the pigment-correcting serum in a circular motion to the entire face

including the forehead, cheeks, chin, nose, and neck with care to avoid the eyes. The Lytera 2.0 is applied prior to applying moisturizer and sunscreen.

On laser treatment days, patients will come into the office without having applied any topical cream that day. Lidocaine topical may or may not be applied over the face avoiding the eyes (lidocaine use will be at discretion of Principal Investigator), and patients will be given protective goggles to shield the eyes during laser treatment. Next, the laser wand is pressed to the face and passed over the skin in various horizontal and vertical directions. Treatment takes 20 to 30 minutes.

Standardized digital photographs will be taken at baseline and at each subsequent visit using the Canfield VISIA Complexion Analysis (VISIA-CA) camera system at the highest resolution in a consistent position. Pictures will be taken before laser treatments on Visit 2 and Visit 3.

The subjects will complete an exit questionnaire after completion of the study at their last study visit (Visit 4). Through the questionnaire, we will obtain information on subject satisfaction with the study as well as their opinion of how their skin has changed. We hope to use the responses to assess efficacy of our skincare regimen and to improve future related research protocols.

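### No photograph, MoPASI, GAIS or exit questionnaire is planned at or after an unscheduled withdrawal, so a subject pulled for severe post-inflammatory skin tone lacks the score that reflects the event

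*Combined protocol and SAP*

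**What the plan says.** - **Trigger.** Section 13 opens its list of mandatory withdrawals with: "If a patient becomes pregnant, develops severe post-inflammatory skin tone, excessive scarring, burning, or experiences an anaphylactic or other" (the list goes on to severe allergic reactions and to infections needing antibiotics). Section 12 also names severe post-inflammatory skin tone.
- **End of the subject's study.** Under Section 8 a subject reaches endpoint either after the exit survey or "if they experience any adverse reactions from treatment and must be pulled from the study".
- **After withdrawal.** Section 13 states: "Participants that develop criteria for withdrawal from the study or any potential side effect will be examined in the office". It then adds: "Safety information will still be collected until week 12 of the study". It mentions no photographs, scales or questionnaires.
- **Meaning of safety information.** Section 12 treats efficacy data, defined by the scale scores, as separate from safety data. Its list of safety items includes changes in skin colour but no scale score or photograph. Safety information may be gathered at visits or by email.
- **Planned measurement.** The Section 7 schedule puts photography, MoPASI and GAIS at all four visits, the self-assessment at Visits 1 and 4, and the exit questionnaire at Visit 4 only. Under Section 9, the Visit 2 and Visit 3 photographs precede that day's laser, and an independent evaluator scores the photographs after all subjects have finished.
- **Analysis.** Section 11: "The primary analyses will be based on the MoPASI and GAIS scores" and "Scores after each laser treatment will be compared to baseline scores using the appropriate statistical test".
- **Sample.** Section 4 keeps in the final study sample those who met the criteria and "did not voluntarily drop out of the study or develop adverse effects that prohibited them from safely completing the study".

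**The concern.** One withdrawal reason is closely tied to what the trial measures. MoPASI grades the area, darkness and pattern of facial pigment, and GAIS has a category for worse. A severe post-inflammatory reaction would probably be a poor result on both. If the reaction appears between scheduled visits, the plan stops outcome measurement at the moment the outcome turns bad.

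Two things are at stake. The first is the between-arm comparison stated in Section 2, which would lose unfavourable results. The second is the effect size that, under Section 11, this pilot is meant to supply for powering a study, since a bias here carries forward. Scores can be computed later from stored photographs, but a photograph never taken cannot be recovered.

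**Working it through.** The plan gives no withdrawal rate, standard deviation, effect size or power, so no figure of its own bears on this point beyond 7 + 7 = 14 subjects. The check is mainly a reading of the schedule.

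**1. What exists, by time of withdrawal** (Sections 7 and 9; photographs come before the laser at Visits 2 and 3)

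- Pulled between Visits 2 and 3: photographs from Visits 1 and 2 only, both pre-laser. There is no post-laser score.
- Reaction found at Visit 3: the scheduled photograph captures it as a score after the first laser.
- Pulled between Visits 3 and 4: the Visit 3 photograph gives a score after the first laser. There is none after the second, and no exit questionnaire or second self-assessment.
- Reaction found at Visit 4: scheduled measurement is complete.

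The gap is therefore detection between visits, plus every scheduled visit after withdrawal. Section 11 compares scores after each laser with baseline, so both post-laser time points matter.

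**2. Does continued safety follow-up fill the gap?** Section 12 separates safety items from scale scores and allows collection by email. Following the plan as written need not produce a photograph, and the evaluator scores only photographs.

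**3. Timing of a possible extra visit.** Visit 4 falls 4 + 3 + 4 = 11 weeks after baseline. That is week 12 if baseline is week 1, which agrees with the weeks 5, 8 and 12 named in Section 9. The planned Visit 4 date thus lies within the safety follow-up.

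**4. Effect of the Section 4 rule.** Subjects stopped by adverse effects are outside the final sample, so even a Visit 3 score already taken is not used.

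**5. Size, by illustration**

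- Share of an arm: 1/7 = 14.3%.
- GAIS mean, assuming six subjects at 2 and a withdrawn one who would score 0: (6 × 2 + 0)/7 = 12/7 = 1.71. Without that subject it is 12/6 = 2.00. The difference is 0.29 of a grade, in whichever arm it occurs.
- Rank test, assuming no ties (the plan names no test): with 6 against 7 and U = 6, the exact two-sided Mann-Whitney p is 0.035. Adding the withdrawn subject at the worst rank puts all 7 of the other arm ahead, so U = 6 + 7 = 13 with 7 against 7, and p is 0.165.
- Chance of at least one withdrawal among 14, at an assumed risk r per subject, is 1 − (1 − r)^14: 25% for r = 2%, 51% for 5%, 77% for 10% and 90% for 15%.

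**The case against.** The strongest reply is that the schedule captures more than it may seem to. Photographs and both scales are planned at every visit, Visit 3 is itself a post-laser time point, and a reaction found at Visit 3 or 4 would be photographed. That stands. A reader might infer that such a subject leaves no scored outcome at all, and the documents do not support this.

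Second, Section 13 does not say that safety information is the only thing collected, and it does not forbid photographs. It also uses both withdrawal from the study and withdrawal from treatment, which leaves room for continued follow-up. This stands in part: the restriction is inferred from Sections 8, 12 and 13 together. But nothing in the plan calls for the missing measurements, and Section 8 treats being pulled as the end for that subject.

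Third, a reader might infer a bias in favour of Lytera because only that arm is exposed to the serum's stinging, redness and irritation. Those effects are not listed by name as withdrawal reasons. Section 14 lists dark spots and pigment changes under the laser, which both arms receive, and if the serum works as hypothesised, pigment withdrawals could be commoner in the other arm. No direction can be claimed.

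Fourth, skin types are limited to I–IV and laser settings are chosen to limit side effects, so the event may be rare. That is fair, and no rate is given. With seven subjects per arm, however, a single case matters.

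**Conclusion.** The point holds in a limited form. A subject pulled between scheduled visits for severe post-inflammatory skin tone has no planned score reflecting the event, and the Section 4 rule discards what was scored before. The loss is related to the outcome, so the arm comparison and the pilot's effect size can be biased, in a direction that cannot be known in advance.

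Only the 14% of an arm per withdrawal is firm. The 0.29 GAIS grade and the change in p from 0.035 to 0.165 rest on assumed scores and ranks, and the chances of a withdrawal rest on assumed risks. That the event would score badly is a reasonable inference from what the scales measure. A reader might go further and call it the worst possible MoPASI result, but the documents do not say so: they do not state that the skin-tone change is a darkening, and lightening would not raise the darkness component.

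This is a cheap improvement worth making. It does not question who is withdrawn.

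**What to change.** Leave the withdrawal triggers unchanged.

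1. Amend Sections 8 and 13 so that stopping study treatment does not end outcome follow-up.
2. At the office examination that Section 13 already requires, take the standard VISIA photographs and give the self-assessment and exit questionnaires.
3. Unless consent is withdrawn, repeat these on the planned Visit 4 date, within the existing follow-up to week 12.
4. Have the independent evaluator score these photographs together with all the others.
5. Amend the final-sample sentence in Section 4 so that all randomised subjects with any scored photograph are analysed in their assigned arm. Without this step the added scores would remain outside the analysis.

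**Cost.** Protocol wording, and one or two extra photograph sessions for the few withdrawn subjects, on the camera already in use. Some may decline to return and would still lack those scores. The Visit 4 scores of those who do return will reflect incomplete treatment, which the report should state.
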